6.2 Time Point Algorithms

6.2.1 Relative Days

6.2.1.1 For Assessments except Adverse Events

For all assessments except adverse events, the following relative day calculation will be used.

The date of randomization will be considered relative day 1, and the day before the randomization will be relative day -1. Relative days will be calculated as follows:

For days on or after randomization:

Date of Assessment – Date of Randomization + 1

For days before randomization:

Date of Assessment – Date of Randomization

6.2.1.2 For Adverse Events

For adverse events, the following relative day calculation will be used.

The start date of sorafenib and the date of first angiogram (whichever occurs first) will be considered relative day 1, and the day before the start date of sorafenib and the date of first angiogram (whichever occurs first) will be relative day -1. Relative days will be calculated as follows :

For days on or after the start date of sorafenib and the date of first angiogram (whichever occurs first):

Date of Assessment – Start date of sorafenib and date of first angiogram (whichever occurs first) + 1

For days before the start date of sorafenib and the date of first angiogram (whichever occurs first):

Date of Assessment – Start date of sorafenib and date of first angiogram (whichever occurs first)

6.2.1.3 Partial Dates

Partial dates with day or day and month missing will be imputed as follows:

- The missing day of onset of an adverse event (AE) will conservatively be set to the earlier of:
 - First day of the month of the AE start month, if the month of the start date of sorafenib and the date of first angiogram (whichever occurs first) is not the same as the AE start month,
 - One day after the start date of sorafenib and the date of first angiogram (whichever occurs first), if the month of the start date of sorafenib and the date of first angiogram (whichever occurs first) is the same as the AE start month.
- The missing day of resolution of an AE will be set to the last day of the month of the AE end month.
- For other variables, including date of tumor response, and progression, partial dates that need to be imputed will use the 15th of the month to replace the missing day.
- A missing day of death will be replaced by the 15th of the month if there are no other assessments after the 15th of the month for that patient. Otherwise the last day of the month will be used to replace the missing day of death.
- If the onset date of an AE is missing both day and month, it will be set to:
 - January 1 of the year of AE start year, if the year of the start date of sorafenib and the date of first angiogram (whichever occurs first) is not the same as the AE start year,
 - One day after the start date of sorafenib and the date of first angiogram (whichever occurs first), if the year of the start date of sorafenib and the date of first angiogram (whichever occurs first) is the same as the AE start year.
- If the resolution date of an AE is missing both day and month, it will be set to December 31 of the AE end year.
- For the date of initial diagnosis of HCC, a missing day will be set to the first day of the month, and a missing day and month will be set to January 1 of the year.
- For the start date of medications recorded on the “Prior and Concurrent Medications” electronic case report form (eCRF) page, a missing day will be set to the first day of the month, and a missing day and month will be set to January 1 of the year. If month/year of the start date (if only missing day) or year of the start date (if missing month/day) is the same as the month/year or year of the randomization date, respectively, the start date will be set to one day after the randomization date.
- For the end date of medications recorded on the “Prior and Concurrent Medications” eCRF page, a missing day will be set to the last day of the month, and a missing day and month will be set to December 31 of the year.
- For the start date of medications recorded on the Best Available Care - Post Treatment Discontinuation – Medication eCRF page and the start date of

procedures recorded on the Additional Procedures eCRF page, a missing day will be set to:

- the first day of the month if the month/year of progression (as determined by the investigator) is not the same as the month/year of the start of best available care medication or additional procedure,
- One day after the date of progression (as determined by the investigator) if the month/year of progression is the same the month/year of the start of best available care medication or additional procedure.
- For the end date of medications recorded on the Best Available Care - Post Treatment Discontinuation – Medication eCRF page and the end date of procedures recorded on the Additional Procedures eCRF page, a missing day will be set to the last day of the month.

6.2.2 Windows

For the purpose of statistical analysis, time windows will need defining for presentations that summarize values by visit. The windows for the visits following baseline will be constructed in such a way that the upper limit of the interval falls half way between the two visits (the lower limit of the first post-baseline visit will be Day 2), as shown below. The assignment of data to visit windows will use the relative day defined in Section 6.2.1.1.

Table 3 Analysis Windows for Assessments Performed at Eight Week Intervals

Week	Scheduled Day	Visit Window for Analysis (Days)
Week 8	57	2 – 85
Week 16	113	86 – 141
Week 24	169	142 – 197
...		
End of Study		Latest assessment available*

*Last assessment should be assigned to a Week X based on the visit windows as well as to the end of study evaluation.

If a patient has more than 1 assessment occurring in the same visit window, the data from the assessment closest to the scheduled day will be used. If 2 assessments have the same distance from the scheduled day, the data of the assessment after the scheduled day will be used. Note that the visit windows will not be used for time-to-event endpoints and subject-level tumor response endpoints (i.e. objective response rate and disease control rate).

6.3 Baseline Assessments

Baseline will be defined as the last non-missing assessment performed on or before the day of randomization.

According to the protocol, the following assessments will be conducted prior to randomization:

- Informed Consent
- Inclusion/ Exclusion Criteria
- Demographics (age, gender, race, ethnicity)
- Medical history
- Physical examination
- Vital signs (heart rate, respiration rate, blood pressure, oral temperature, height and weight)
- Disease and treatment history
- ECOG performance status
- Laboratory tests (hematology, coagulation, chemistry)
- Serum pregnancy test
- Child Pugh Score
- HCC tumor biomarkers
- Liver volume/mass and tumor burden
- FACT-hep QOL
- CT/MRI of chest, abdomen, and pelvis
- Stratification factors: region (North America and Europe vs Asia), ECOG performance status (0 vs 1), presence or absence of branch PVT

Time from diagnosis of HCC will be calculated as follows:

Time from diagnosis of HCC (in months) = (Date of Randomization – Date of Diagnosis)/30.4375.

6.4 Efficacy Variables

For all efficacy evaluations, the baseline measurement is defined as the last measurement on or prior to the date of randomization. Any tumor assessments performed within 6 weeks of randomization are less accurate for tumor response assessment, so will not be included in the analysis of imaging related efficacy endpoints.

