5.2.2 Secondary Endpoints

In Version 5.0 of the protocol dated Jan 8th 2016, a sequential hierarchical approach was added to control the study-wise Type I error rate. Also, in Version 5.0 supportive analyses were added using the Cox regression model to evaluate the effect of multiple covariates, including stratification factors, on the secondary efficacy time-to-event endpoints.

In the current protocol, section 10.2.3.2 states that time to progression (TTP) will be calculated as the interval between the randomization date and the date of first disease progression, including death for any cause. However, death will not be considered as a TTP event. Section 6.4.2.2 of this SAP explains how TTP will be analyzed.

In the current protocol, sections 10.2.3.1 and 10.2.5 state that tumor response rate per RECIST 1.1 by investigator determination and per mRECIST by blinded centralized independent imaging assessment will be compared between treatment arms using the continuity adjusted Newcombe-Wilson test. However, the continuity adjusted Newcombe-Wilson approach only provides confidence intervals and not p-values. Hence, the continuity adjusted Wald approach will be used instead, which provides both confidence intervals and p-values.

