6.4.2.2 Time to Progression according to RECIST v1.1 criteria by investigator determination

This secondary endpoint is time to progression. TTP is defined as the time from date of randomization until date of radiological progression according to RECIST v1.1 criteria by investigator determination.

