8.6.2.1 Time to Progression (TTP) according to RECIST v1.1 criteria by investigator determination

TTP rates will be derived from the Kaplan-Meier estimates for each treatment group; 3, 6, 9, and 12-month TTP rates will be presented, together with 95% CIs. Quartiles will be presented and 95% CIs will be calculated on the quartiles for each treatment group. A log-rank (two-sided) test will be used to compare TTP between the two treatment groups at a 0.05 significance level. The HR and corresponding 95% CI will be computed from a Cox proportional hazards model. Plots of the Kaplan-Meier curves will be provided for each treatment group. This analysis will be performed on both the mITT and PP populations.

$$\text{TTP (Months)} = (\text{Date of event/censor} - \text{Date of Randomization} + 1) / 30.4375.$$

The censoring is performed in the following order:

- 1) If a patient does not have a baseline tumor assessment, then the TTP time will be censored at the randomization date, regardless of whether or not radiological disease progression (i.e. PD) has been observed.
- 2) If a patient received a subsequent HCC therapy before PD or in the absence of PD, the TTP time will be censored at the last valid (i.e. evaluable) post baseline radiological tumor assessment on or before the start date of the subsequent HCC therapy. If the patient has no valid post-baseline radiological tumor assessments on or before the start date of the subsequent HCC therapy, the patient will be censored at the randomization date.
- 3) If a patient is known not to have PD and did not receive subsequent HCC therapy, the TTP time will be censored at the date of death* or last valid post baseline radiological tumor assessment date in the absence of death, or at the randomization date if the patient does not have any valid post-baseline radiological tumor assessments or death.
- 4) If a patient had PD immediately after two or more missed visits (Note: a response of NE at a visit is not considered as a missed visit), the patient will be censored at the time of the last valid post baseline radiological tumor assessment date that occurred before the missed visits. If the patient has no valid post-baseline radiological tumor assessments before the missed visits, the patient will be censored at the randomization date.

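### The 6-week scan exclusion in SAP 6.4 is justified for response only, yet it also removes documented early progression from TTP and PFS

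*SAP*

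**What the plan says.** SAP 6.4 (Efficacy Variables) gives the reason first: "Any tumor assessments performed within 6 weeks of randomization are less accurate for tumor response assessment". It then draws the consequence for all such assessments: "so will not be included in the analysis of imaging related efficacy endpoints". It makes no exception for progressive disease, new lesions or extra-hepatic lesions.

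TTP is an imaging endpoint. In SAP 6.4.2.2, "TTP is defined as the time from date of randomization until date of radiological progression according to RECIST v1.1 criteria by investigator determination". SAP 5.2.2 adds: "However, death will not be considered as a TTP event". PFS (SAP 6.4.3.5, 6.4.3.6 and 8.6.6) also uses imaging progression, but counts death as an event.

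The third TTP censoring rule in SAP 8.6.2.1 applies "If a patient is known not to have PD and did not receive subsequent HCC therapy"; in that case "the TTP time will be censored at the date of death* or last valid post baseline radiological tumor assessment date". A note to these rules plans a sensitivity analysis that replaces censoring at death by censoring at the last valid scan.

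The protocol (10.2.2.2 and 10.2.3.2) measures TTP to the first progression, counts new liver and extra-hepatic lesions, and has no 6-week exclusion.

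**The concern.** A scan taken soon after treatment may measure shrinkage poorly. That is a sound reason to keep it out of a response rate. It is not a reason to ignore a new lesion or new extra-hepatic disease, which the protocol counts as progression. As worded, the SAP treats both alike.

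At stake is the date, and sometimes the existence, of the earliest progression events in a secondary endpoint (TTP) and an additional one (PFS). SAP 5.2.2 records another departure from the protocol's TTP, namely that death is no longer an event. The readable subsections of SAP 5.2 do not record this one (5.2.4 is blacked out). No planned analysis shows the result with the early progressions kept.

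**Working it through.** The plan attaches no figure to this rule, so there is none to reproduce. The check applies the SAP's rules to a patient whose progression (PD) was documented within 6 weeks.

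**1. What happens once the early scan is dropped**

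| Later course | TTP (SAP 8.6.2.1) | PFS (SAP 8.6.6) |
|---|---|---|
| No later PD, no subsequent HCC therapy, death | Censored at death (rule 3) | Event at death |
| Subsequent HCC therapy before any later PD | Censored at last valid scan before it, or at randomization if none (rule 2) | Same (rule 2) |
| First remaining scan shows PD, two or more visits missed (16 weeks from randomization) | Censored at randomization (rule 4) | Same (rule 4) |
| PD on a timely later scan | Event at the later date | Event at the later date |

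The early PD date is lost in every row. Rule 3 fits poorly, since it describes a patient known to be free of PD, but no other rule covers the first row.

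**2. Example (hypothetical patient)**

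PD 30 days after randomization, no later scan, no subsequent HCC therapy, death at day 150. The SAP formula is (days + 1)/30.4375.

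- As written: TTP censored at 151/30.4375 = 4.96 months; PFS event at 4.96 months.
- With the early PD counted: TTP and PFS events at 31/30.4375 = 1.02 months.
- Planned TTP sensitivity analysis: no valid scan remains, so the patient is censored at randomization. The time is no longer overstated, but the event is still missing.

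**3. Which scans are reached**

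SAP 6.2.2 puts Week 8 at relative Day 57. The permitted 14 days earlier give Day 43. Randomization is Day 1, so this is 42 days, exactly 6 weeks, after randomization. On-schedule scans are therefore outside the exclusion, except possibly at day 42, which the wording leaves open. Essentially only unscheduled scans are affected.

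**4. Size**

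Assume exponential TTP with the 5.5-month median quoted for sorafenib in protocol 5.3. Six weeks is 42/30.4375 = 1.38 months, and 1 − 2^(−1.38/5.5) = 0.16. For medians of 10 and 2.8 months the share is 0.09 and 0.29. This is true progression by week 6; only the part found on an early scan is affected, and the documents do not give that part. If 1% to 5% of the 468 effective patients in SAP Appendix 5 had such a scan (assumption), that is 468 × 0.01 ≈ 5 to 468 × 0.05 ≈ 23 patients.

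**5. Effect on the comparison (illustration)**

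Simulation with no true difference: 234 patients per arm, median TTP 5.5 and OS 10.7 months, independent and exponential, with scans every 8 weeks. An assumed share q of those progressing within 6 weeks is found on an early scan and is neither scanned again nor given subsequent therapy. The ratio is TTP events per person-time, TheraSphere over control; simulation noise is about 0.01.

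| q control / TheraSphere | Ratio, early PD dropped | Ratio, early PD counted | Events lost |
|---|---|---|---|
| 10% / 10% | 1.00 | 1.00 | about 7 of 291 |
| 30% / 30% | 1.00 | 1.00 | about 22 of 292 |
| 5% / 20% | 0.91 | 1.01 | about 9 of 291 |
| 10% / 30% | 0.90 | 1.01 | about 14 of 291 |

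The arms are otherwise identical, so swapping the shares gives roughly the reciprocals, 1/0.91 = 1.10 and 1/0.90 = 1.11. Equal shares cost events; unequal shares bias the ratio, in a direction set by an unknown input.

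**The case against.** The strongest defense is that the rule is pre-specified, applies to both arms, reaches almost no scheduled scan and leaves the primary endpoint alone. TTP is confirmatory only if OS succeeds (SAP 8.6.2). Protocol 9.2.16 calls for scans every 8 weeks until death, so persistent progression would usually be counted a few weeks late rather than lost. If one arm had more incidental early scans, dropping them would even out ascertainment. All of this stands, and it limits the size of the point. It does not explain why a reason about response should govern new lesions, or why no analysis shows the alternative. Loss of later scans is also plausible: protocol 9.1.2.2 and 9.1.3.5 provide telephone contact for patients who stop treatment for progression and cannot attend.

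A reader might infer more than the documents support:

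- **That the visit windows contradict the exclusion.** SAP 6.2.2 says "the lower limit of the first post-baseline visit will be Day 2", which overlaps the excluded weeks. The same section states that the windows do not apply to time-to-event endpoints, ORR or DCR. Only PTTS and by-visit tumor summaries need a clarifying phrase.
- **That the rule favors TheraSphere.** The extra procedures scheduled in that arm in weeks 1-8 are angiography and 99mTc-MAA for planning. Efficacy scans follow the same 8-week schedule in both arms, so more early RECIST assessments in one arm are not established.
- **That early progressors generally gain many progression-free months.** This needs no later PD scan and no subsequent HCC therapy. It concerns the main TTP analysis; the planned sensitivity analysis removes the extra time, and death remains a PFS event.
- **That the same early progression still defines the safety and Per Protocol sets.** SAP 8.3.2 and 8.3.3 use investigator progression without mentioning the exclusion, but do not say how it applies there.

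**Conclusion.** The exclusion is broader than its stated reason, departs from the protocol's TTP without a readable entry in SAP 5.2, and discards the date of any progression documented in the first 6 weeks. The planned TTP sensitivity analysis changes only censoring at death and does not restore the event.

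The consequence is probably small. It depends on how many patients had an unscheduled early scan showing progression, which the documents do not report; the 5 to 23 patients and all simulated shares are assumptions. OS, TTSP and quality of life are unaffected. TTUP is affected at most in part, because it also has clinical triggers and uses an investigator eCRF answer. The direction of any bias between arms cannot be determined. This is a worthwhile, low-cost correction and not a threat to the trial's main conclusion.

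**What to change.** 1. Limit the 6-week exclusion in SAP 6.4 to response endpoints (ORR, DCR, depth of response, PTTS). State that it means after randomization, and whether day 42 is in or out.
2. Count investigator PD by new or extra-hepatic lesions at any date as a TTP and PFS event.
3. Add two sensitivity analyses of TTP and PFS: one counting all PD within 6 weeks, including target-lesion growth, and one using the current rule.
4. Report by arm the number of excluded scans and the number showing PD.
5. List the departure from the protocol in SAP 5.2.
6. For PTTS and by-visit tumor summaries only, state that the exclusion is applied before the Day 2-85 window.

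The cost is SAP wording and a re-run on data already collected. The downside is that a few early pseudo-progressions, or early scans obtained unequally between arms, may count; the paired sensitivity analyses and the counts by arm would show how much that matters.

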6.4.1 Primary Efficacy Variable – Overall Survival (OS)

The primary study endpoint is OS, which is defined as the time from date of randomization until date of death due to any cause.

6.4.2 Secondary Efficacy Variables

The secondary efficacy endpoints for this study are:

- Tumor Response, defined as Objective Response Rate (ORR) according to RECIST v1.1 criteria by investigator determination
- Time to Progression (TTP) according to RECIST v1.1 criteria by investigator determination
- Quality of Life Assessments
- Time to Untreatable Progression (TTUP)

- Time to Symptomatic Progression (TTSP)

6.4.2.1 Objective Response Rate (ORR) according to RECIST v1.1 criteria by investigator determination

Tumor Response is based on the radiological tumor assessment performed at specified time points. The post baseline assessments are compared to the baseline assessment and the overall response based on investigator assessment according to RECIST criteria v1.1 is recorded at each efficacy visit. The tumor response for target lesions is categorized as Complete Response (CR), Partial Response (PR), Stable Disease (SD), Progressive Disease (PD) or Not all Evaluated (NE) according to the RECIST criteria v1.1² as shown in Table 4. Table 5 shows the responses for non-target lesions.

Table 4: Target lesion response categories

Response	Definition
Complete Response (CR)	Disappearance of all target lesions
Partial Response (PR)	$\geq 30\%$ decrease in the sum of the diameters of target lesions
Stable Disease (SD)	Neither CR nor PR nor PD
Progressive Disease (PD)	$\geq 20\%$ increase in the sum of the longest diameter of target lesions from smallest value on study The sum of diameters must also demonstrate an absolute increase of at least 5 mm, e.g. two lesions increasing from 2 mm to 3 mm does not qualify
Not all Evaluated (NE) ^a	When imaging/measurement is not done at all at a particular time point, the patient is not evaluable (NE) at that time point. If only a subset of lesion measurements is made at an assessment, usually the case is also considered NE at that time point, unless a convincing argument can be made that the contribution of the individual missing lesion(s) would not change the assigned time point response.

Source: Protocol version 7.0, 22-Jul-2019; ^aSource: Eisenhauer et al (2009)²

Table 5: Non-target lesion response categories

Response	Definition

CR	Disappearance of all non-target lesions All non-target lymph nodes must be non-pathological in size (<10 mm short axis)
Non-CR/Non-PD	Persistence of 1 or more non-target lesions
PD ^a	Unequivocal progression of existing non-target lesions
Not Evaluable (NE) ^a	When no imaging/measurement is done at all at a particular time point, the patient is not evaluable (NE) at that time point. If only a subset of lesion measurements are made at an assessment, usually the case is also considered NE at that time point, unless a convincing argument can be made that the contribution of the individual missing lesion(s) would not change the assigned time point response.

^a According to Eisenhauer et al (2009)² “to achieve ‘unequivocal progression’ on the basis of the non-target disease, there must be an overall level of substantial worsening in non-target disease such that that, even in presence of SD or PR in target disease, the overall tumor burden has increased sufficiently to merit discontinuation of therapy. A modest ‘increase’ in the size of one or more non-target lesions is usually not sufficient to qualify for unequivocal progression status.”

Source: Eisenhauer et al (2009)²

Table 6 provides a summary of the overall response status calculation at each timepoint.

Table 6: Timepoint response

Target lesions	Non-target lesions	New lesions	Timepoint response
CR	None	No	CR
PR	None	No	PR
SD	None	No	SD
PD	None	No	PD
Any	None	Yes	PD
CR	CR	No	CR
CR	Non-CR/Non-PD	No	PR
CR	Not evaluated	No	PR
PR	Non-PD or not all evaluated	No	PR
SD	Non-PD or not all evaluated	No	SD
Not all evaluated	Non-PD	No	NE
PD	Any	Yes or No	PD
Any	PD	Yes or No	PD
Any	Any	Yes	PD

None	CR	No	CR
None	Non-CR/Non-PD	No	Non-CR/Non-PD
None	Not at all evaluated	No	NE
None	Unequivocal PD	Yes or No	PD
None	Any	Yes	PD

Source: eCRF

The best overall response is based on the overall responses from each imaging assessment according to RECIST 1.1. It is the best response a patient has had following randomization, but up to and including the first PD or the last valid post baseline imaging assessment in the absence of the first PD.

If a patient received a subsequent systemic anticancer treatment (excluding sorafenib) and/or non-protocol liver directed therapy (excluding ablation/surgery) (henceforth referred to as “subsequent HCC therapy” in this document for ease of reference; see Appendix 4 for details), tumor response assessments after the start date of the subsequent HCC therapy will be excluded from the calculation of best overall response.

The ORR is defined as the proportion of randomized patients achieving a best overall response of CR or PR.

Patients who do not have any post baseline tumor assessments for any reason on or prior to the start date of the subsequent HCC therapy, are considered non-responders and are included in the denominator when calculating the ORR.

